9.2.2 Primary endpoint(s) analyses

9.2.2.1 Definition of endpoint(s)

The two co-primary endpoints are the change from baseline to Week 24 in bilateral endoscopic NPS and in NCS.

9.2.2.2 Main analytical approach

The 2 co-primary endpoints will be analyzed with the primary estimand defined according to the following attributes:

- Endpoint: change from baseline to Week 24 in NPS and NCS.
- Intervention condition: itepekimab 300 mg Q2W and itepekimab 300 mg Q4W will be compared to placebo, on top of background therapy.
- Analysis population: intent-to-treat (ITT) population.
- Intercurrent events:
 - The following IEs will be handled with a composite variable strategy. Data after the IE will be assigned to the worst possible score:
 - a) Use of selected prohibited/rescue medication (eg, prohibited biologic therapy) prior to Week 24.
 - b) Nasal/sinus surgery prior to Week 24.

- The following IEs will be handled with a treatment policy strategy. All assessments after starting such IE and before or at Week 24 will be included:
 - a) Use of SCS for any reason.
 - b) Study intervention discontinuation.
 - c) Use of other prohibited/rescue medications prior to Week 24.
- Population-level summary: difference in LS means between itepekimab and placebo from ANCOVA model with change from baseline to Week 24 in NPS and NCS as response variables, intervention group (itepekimab 300 mg SC Q2W, itepekimab 300 mg Q4W, or placebo) and randomization stratification factors (asthma/AERD status and regions) as fixed effects, and the baseline value as covariates. The corresponding 95% CI will be provided along with the p-value. In addition, descriptive statistics including number of participants, mean, SEM, and LS means will be provided for each intervention group.
- Missing data handling.

After applying the rules for IEs, if there is still missing data, then the missing data will be handled as follows:

- For participants who discontinue IMP before Week 24 without use of selected prohibited/rescue medication (eg, prohibited biologic therapy) or nasal/sinus surgery prior to Week 24: MI approach will be used to impute missing endpoint value at Week 24, and this MI will use all participants from the same randomized arm, excluding participants who use selected prohibited/rescue medication (eg, prohibited biologic therapy) or nasal/sinus surgery prior to Week 24.

Each of the imputed complete data will be analyzed by fitting the ANCOVA model. Statistical inference obtained from all imputed data will be combined using Rubin's rule.

9.2.2.3 Sensitivity analyses

The reason and pattern of missing data will be carefully examined. Sensitivity analyses will be performed to confirm robustness of the results with respect to the missing data handling strategy in addition to the primary estimand. In particular, a sensitivity analysis will be performed using a control-based (ie, jump to reference) pattern mixture model by multiple imputation (PMM-MI) for missing data. Details of the sensitivity analyses will be provided in the SAP.

9.2.2.4 Supplementary analyses

Supplementary analyses will be performed, eg, to confirm robustness of the results with respect to the IE handling strategy in addition to the primary estimand. In particular, a supplementary analysis will be performed considering a composite strategy for handling the use of SCS for any reason, the use of selected prohibited/rescue medication (eg, prohibited biologic therapy) and nasal/sinus surgery prior to Week 24 (data after the IE will be assigned to the worst observation carried forward [WOCF]). In addition, a supplementary analysis will be performed considering a treatment policy strategy to handle all the IEs. Details of the supplementary analyses will be provided in the SAP.

9.2.3 Secondary endpoint(s) analyses

The secondary endpoints detailed in this section are as follows:

- **Continuous efficacy endpoints** including change from baseline in NPS and in NCS at Week 52, change from baseline in LMK score at Week 24, change from baseline in TSS, in Loss of Smell Symptom Severity score, in UPSIT score, in SNOT-22 total score and PROMIS SD-SF-8b score at Week 24 and Week 52: these endpoints will be analyzed in the same fashion as the co-primary endpoints described in [Section 9.2.2.2](#).
- **Proportion endpoints**, including proportion of participants with CRSwNP requiring SCS or surgery for CRS during the planned study intervention period and proportions of NPS responders, will be analyzed using an MH method stratified by asthma/AERD strata and region. The estimate of the MH weighted risk difference and corresponding Wald 95% confidence interval and Wald test using Sato variance will be provided. All data collected after study intervention discontinuation will be used in the analysis. Participants who discontinue the study without an event will be considered as no event.
- **Time to first SCS use or surgery for CRS** will be analyzed using a Cox regression model. The time to the first event will be included as the dependent variable while intervention group, asthma/AERD strata and region will be used as covariates. The HR will be estimated for comparison of each Itepekimab regimen to placebo. The Kaplan-Meier method will be used to derive the probabilities that a participant would experience an event up to specific time points for each intervention group.
- **The annualized number of SCS course or surgery for CRS** during the planned study treatment will be analyzed using a negative binomial regression model. The model will include the number of SCS course or surgery for CRS during the planned study treatment period as the response variable, with intervention group, asthma/AERD strata and regions. Log transformed treatment duration will be the offset variable. The estimated annualized number of SCS courses or surgery for CRS for each treatment group and its 95% CI will be derived from the negative binomial model. The event rate ratio of each Itepekimab regimen versus placebo and the corresponding 95% CI and p-values will be provided.
- **Changes from baseline to Week 24 and 52 in pre-BD FEV1 and in ACQ-5 score** will be analyzed in participants with comorbid-asthma. These endpoints will be analyzed in the same fashion as for the coprimary endpoints without the asthma/AERD strata as a covariate in the model.
- **The following efficacy endpoints will be analyzed in participants with AERD**, in the same fashion as the one considered on the entire population without the asthma/AERD strata as a covariate in the model.
 - Change from baseline to Week 24 and 52 in NPS, NCS, pre-BD FEV1 and ACQ-5 score.
 - The proportion of participants requiring SCS or surgery for CRS during the planned study intervention period.
 - Annualized rate of SCS or surgery for CRS during the planned study intervention period.

- Time to first either SCS or surgery for CRS.

Other secondary endpoints analyses are defined in [Section 9.2.6.1](#) (AE, SAE), [Section 9.2.6.2](#) (laboratory abnormalities), [Section 9.2.7](#) (PK, immunogenicity).

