
 To evaluate the efficacy of itepekimab compared to placebo. To evaluate the safety and tolerability of itepekimab compared to placebo in participants with CRSwNP. To evaluate the PK of itepekimab. Assessment of immunogenicity to itepekimab over time compared to placebo. 	
 Annualized rate of SCS course or surgery for CRS during the planned study intervention period in participants with AERD. Time to first either SCS or surgery for CRS in participants with AERD. Change from baseline to Weeks 24 and 52 in pre-BD FEV1 (in mL) in participants with AERD. Proportion of NPS responders at Weeks 24 and 52 (defined as participants with improvement by at least 1 point in NPS). Proportion of NPS responders at Weeks 24 and 52 (defined as participants with improvement by at least 2 points in NPS). Incidence of TEAEs, TESAEs, TEAESIs and TEAEs leading to treatment discontinuation. Itepekimab concentration in serum. Incidence of treatment-emergent anti-itepekimab antibody (ADA) responses throughout the study.
Tertiary/Exploratory	

 To evaluate the effect of itepekimab on overall health status, cough, PGIS and PGIC. To evaluate the efficacy of itepekimab compared to placebo in CRSwNP quality of life. To evaluate the effects of itepekimab compared to placebo on total sinus opacification. To evaluate the effect of itepekimab on health care resource use/productivity compared to placebo. To evaluate the early effect of itepekimab compared to placebo on lung function and asthma in the subgroup of participants with co-morbid asthma. 	
 Change from baseline to Weeks 24 and 52 in the EQ-5D index and VAS. Change from baseline to Weeks 24 and 52 in PGIS score for each symptom and for symptoms overall. PGIC score at Weeks 24 and 52 for each symptom and for symptoms overall. Change from baseline to Weeks 24 and 52 in Leicester Cough Questionnaire total score. Proportion of SNOT-22 responders at Weeks 24 and 52 (defined as participants with improvement of at least 8.9 points in SNOT-22). Change from baseline to Week 24 in sinus (all sinuses) percent opacification volume assessed by CT scan. Cumulative number of health care resource utilization by visit type. Change from baseline to Weeks 24 and 52 in WPAI-SHP on overall work impairment and daily activity impairment. Change from baseline to Weeks 4 in pre-BD FEV1.

Objectives	Endpoints

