6.9.1 Rescue therapy

During the study treatment and follow-up periods, based on clinical evaluation, in case of worsening of signs and/or symptoms/acute sinusitis requiring medical intervention, the Investigator may consider rescue treatment with:

- Systemic antibiotics (up to 2 weeks) in case of acute infection.
- Short course SCS (prednisone or equivalent prednisolone up to 7 days; avoid use 4 weeks before Week 24 or Week 52, if possible).
- Sinonasal surgery for CRSwNP (8 weeks of IMP treatment is recommended prior to surgery to allow onset of treatment effect).

Participants receiving rescue treatment other than surgery during the study should continue on study drug unless the Investigator decides to withdraw the study treatment. Before starting treatment with SCS participants should come to the study site for the clinical assessments. It is recommended to avoid use of SCS as rescue therapy during the Week 20 to Week 24. If a participant must use SCS during this period to control worsening of symptoms based on Investigator judgment the site should make every effort to schedule the Week 24 CT scan prior to SCS rescue therapy. For participants who undergo or are planned for surgery for CRSwNP, the Investigator may decide to continue IMP up to the time of surgery or EOT, whichever date

comes first. At the time of surgery participants will be permanently discontinued from study intervention and assessed as soon as possible using the procedures normally planned for the EOT visit. In any case participants who prematurely discontinued the intervention will be encouraged to return to the study site for the efficacy and safety assessments planned at EOT visit and for additional visits. Additional appropriate medical/therapy per local guideline or per Investigators decision may be considered to use as rescue medicine.

The date and time of rescue medication administration as well as the name and dosage regimen of the rescue medication must be recorded in the eCRF.

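### As written, the NPS responder analysis can count a participant whose polyps were surgically removed as a responder, while the NPS change analysis gives that participant the worst score

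*Protocol*

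**What the plan says.** Section 3 (Table 2) sets two responder endpoints at Weeks 24 and 52: "defined as participants with improvement by at least 1 point in NPS" and "defined as participants with improvement by at least 2 points in NPS". Neither definition mentions surgery or rescue treatment.

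Section 9.2.3, repeated in the Synopsis (Section 1.1), treats these in the same bullet as the proportion needing SCS or surgery. The "proportions of NPS responders, will be analyzed using an MH method stratified by asthma/AERD strata and region". The bullet then gives two data rules for everything in it: "All data collected after study intervention discontinuation will be used in the analysis" and "Participants who discontinue the study without an event will be considered as no event".

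The bullet just before it, on continuous endpoints, refers back to Section 9.2.2.2. There, surgery and selected prohibited/rescue medication are composite events: "Data after the IE will be assigned to the worst possible score". The proportion bullet has no such reference.

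On surgery itself, Section 6.9.1 says: "At the time of surgery participants will be permanently discontinued from study intervention". Section 7.1.1 asks participants who stop IMP to attend the remaining visits, and the Schedule of Activities (Section 1.3) places endoscopy at Weeks 24 and 52.

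**The concern.** The bullet joins two endpoints that run in opposite directions. For the SCS/surgery proportion, surgery is the event and using all later data is natural. For NPS response, the event is a success, and surgery lowers the NPS mechanically. Using all data after IMP discontinuation, with no rule for surgery, lets the operation itself produce the response.

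Two things are at stake. First, an NPS responder rate that includes surgical removal of polyps is hard to read as a drug effect. Second, the same participant can be the worst outcome in one NPS analysis and a success in another at the same visit. Section 2.3.2 hypothesises less rescue SCS and surgery on itepekimab, and Section 3 makes that a secondary objective, so misclassified responders would be expected mainly on placebo.

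**Working it through.** **The plan's own figures.** Section 9.4 states 95% power for each co-primary endpoint with 70 per arm and two-sided alpha 0.049. With noncentrality |difference| / (SD × √(2/n)):
- NPS: 1.10 / (1.79 × √(2/70)) = 3.64, power 95.0%.
- NCS: 0.55 / (0.9 × √(2/70)) = 3.62, power 94.8%.

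The minimal detectable differences are 0.60 and 0.30, and joint power under independence is 0.90. The stated figures reproduce. The present point does not depend on them: no power is stated for the responder endpoints, and only n = 70 per arm is used below.

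**Following one participant through the text.**
1. Entry requires NPS of at least 5 out of 8 (Section 5.1, I 04), so a fall of 1 or 2 points is open to everyone.
2. Suppose baseline NPS is 6 (illustrative), with surgery before Week 24. IMP stops permanently (Section 6.9.1).
3. The participant attends Week 24 and NPS is 3 (illustrative).
4. NPS change analysis (Section 9.2.2.2): the score is set to 8, so the change is 8 − 6 = +2.
5. Responder analysis (Section 9.2.3): the observed 3 is data after IMP discontinuation and is used. The change is 3 − 6 = −3, a response on both cut-offs.

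This needs three conditions: the participant stays in the study, has an endoscopy after surgery, and meets the cut-off. A participant who is operated on and then leaves the study counts as no event.

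**Size.** Each such participant moves an arm's responder rate by 1/70 = 1.4 percentage points. The protocol gives neither a surgery rate nor a placebo responder rate, so the table is illustrative. The active rates (65% and 46%) are the dupilumab figures in Section 2.1, used as stand-ins; placebo rates of 30% and 15% and the surgery rates are assumptions. Every operated participant is taken to meet the cut-off when data are used as observed.

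Difference as observed = (active rate + active surgery) − (placebo rate + placebo surgery). Power is for an unstratified comparison of two proportions, 70 per arm, two-sided alpha 0.049.

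| Surgery, active/placebo | ≥1 point: difference | Power | ≥2 points: difference | Power |
|---|---|---|---|---|
| Counted as non-response | 65 − 30 = 35 | 99% | 46 − 15 = 31 | 98% |
| 1% / 5% | 66 − 35 = 31 | 96% | 47 − 20 = 27 | 93% |
| 2% / 10% | 67 − 40 = 27 | 90% | 48 − 25 = 23 | 81% |
| 3% / 15% | 68 − 45 = 23 | 79% | 49 − 30 = 19 | 63% |
| 5% / 5% | 70 − 35 = 35 | 99% | 51 − 20 = 31 | 98% |

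With lower assumed placebo response (15% for ≥1 point, 5% for ≥2 points), the three unequal scenarios shrink the difference by the same 4, 8 or 12 points, but power stays at about 96% or more.

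**The case against.** The strongest reply is that the all-data sentence addresses IMP discontinuation only. Section 9.2.2.2 also handles discontinuation by treatment policy and still applies the worst-score rule after surgery, so the two rules can coexist. On that view Section 9.2.3 is merely silent on surgery for responders. Section 9 describes itself as a summary, and the SAP, which is not at hand, may supply a non-responder rule. Part of this stands: nothing in the protocol prevents such a rule. But Section 9.2.3 does more than defer. It fixes a data rule, sends only the continuous endpoints to Section 9.2.2.2, and leaves the responder definition without a surgery condition. Someone programming from this text would count the operated participant as a responder.

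A second reply is that Section 9.2.2.4 already plans a treatment-policy analysis of NPS across all intercurrent events, so a responder analysis on the same footing would be a different estimand rather than an error. That is fair as logic, but there it is labelled supplementary; here it would be the only stated analysis, with no sign that the change of estimand was intended.

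The caveats on size also stand. Visits after IMP discontinuation are encouraged but may be reduced (Section 7.1.1), and Section 6.9.1 recommends 8 weeks of IMP before surgery, which limits how many operations fall before Week 24.

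**Conclusion.** The point holds for surgery. Read literally, Sections 9.2.3 and 1.1 let a post-operative fall in NPS count as response, against the plan's own composite strategy for the same measurement. The size is up to 1.4 points of responder rate per operated participant. The dilution is 4 to 12 points under the assumed unequal surgery rates, and nil if surgery is equal across arms.

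Four stronger readings that a reader might infer are not supported:
- That prohibited biologics are caught by the quoted sentence in the same way. Section 7.1.1 allows temporary discontinuation and resumption of IMP, so the sentence need not apply. For biologics the gap is only the missing intercurrent-event rule.
- That the trial risks a false-positive finding. With more surgery on placebo the effect is dilution.
- That a main result is affected. NPS responders are neither co-primary nor key secondary, and Section 9.2.5 leaves the list of tested secondary endpoints to the SAP, so a confirmatory role is not established.
- That counting early leavers as no event is a fault in the SCS/surgery proportion. It is an explicit convention, and Section 9.2.3 also analyses those events by Cox regression with Kaplan-Meier estimates and by negative binomial regression with a duration offset.

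This is a modest correction, best made before unblinding.

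**What to change.** In Sections 9.2.3 and 1.1, separate the two kinds of proportion endpoint. For NPS responders, state that a participant with nasal/sinus surgery or a selected prohibited/rescue medication before the analysis timepoint (Week 24 or Week 52, as applicable) is a non-responder, in line with the composite strategy of Section 9.2.2.2. This also closes the gap for biologics. Keep the all-data sentence and the no-event rule for the SCS/surgery proportion, where they fit. The SAP should carry the same rule.

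The cost is wording only: no new data, visits or participants. Responder rates would be slightly lower in any arm with rescue surgery than under the text as it stands.

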- g* Past medical history including allergic comorbidities (asthma, aspirin sensitivity, allergic rhinitis etc), surgeries will be assessed including type and dates of sinonasal surgeries in the past. SCS use (number of courses, doses, way of administration and duration) in the past 2 years before Visit 1 and/or contraindication/intolerance to SCS, as well as long-term antibiotics use (>2 weeks) in the previous year will be entered in the eCRF.
- h* See Appendix 14 [Section 10.14](#) for AERD screening questionnaire.
- i* Details on actual or planned date, type, and outcome (whenever possible) of surgery will be recorded in a specific eCRF page. If surgery is performed during the study intervention period or follow-up, an AE or SAE page will be completed. Participants will be discontinued from study intervention and assessed as soon as possible using the procedures normally planned for the EOT visit. If surgery is scheduled after the planned EOS, a follow-up contact(s) may be required to document the surgery date and outcome.
- j* Nasal endoscopy (including use of decongestants before the procedure) will be performed after all other efficacy assessments have been completed for each visit and prior to IMP administration. Standard video sequences will be downloaded by the investigator to the central reader's secured Internet site. For eligibility central reading of Visit 1 will be used. At Visit 2 investigator reviews Visit 1 results from central reader to confirm inclusion criteria. Investigator then reconfirms eligibility based on review of Inclusion/Exclusion Criteria and by investigator's Visit 2 endoscopy local reading. This local read is solely for the purpose of confirming eligibility. The Visit 2 endoscopy will then be centrally read for NPS determination for outcome assessment.

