5.1 INCLUSION CRITERIA

Participants are eligible to be included in the study only if all of the following criteria apply:

Age

I 01. Participants must be 18 years of age or older, at the time of signing the informed consent.

Type of participant and disease characteristics

I 02. Participants with a history of CRSwNP for at least 1 year prior to screening.

I 03. Participants must have at least one of the following features:

- Prior sinonasal surgery for NP.
- Worsening symptoms of CRS requiring treatment with SCS within the prior 2 years before screening (Visit 1).
- Worsening symptoms of CRS in the past 2 years which would have required treatment with SCS, however participant is intolerant or has a contraindication to SCS.

I 04. An endoscopic bilateral NPS of at least 5 out of maximum score of 8 (with a minimum score of 2 in each nasal cavity) at screening and randomization.

I 05. Ongoing symptoms (for at least 12 weeks before Visit 1) of:

1. Nasal congestion/blockade/obstruction with moderate or severe (symptom severity score 2 or 3) at Visit 1 and a weekly average severity of greater than 1 in the week before randomization (Visit 2),

AND

2. At least one of the following two symptoms: loss of smell or rhinorrhea (anterior/posterior).

Weight

Not applicable.

Sex, contraceptive/barrier method and pregnancy testing requirements/breastfeeding.

I 06. All

Contraceptive use by men and women should be consistent with local regulations regarding the methods of contraception for those participating in clinical studies.

a) Male participants:

- No contraceptive measures required for this study.

b) Female participants

- A female participant is eligible to participate if she is not pregnant or breastfeeding, and at least 1 of the following conditions applies:
 - Is not a WOCBP
- OR
- Is a WOCBP and agrees to use a contraceptive method that is highly effective, with a failure rate of <1%, as described in Appendix 4 ([Section 10.4](#)) during the study (at a minimum until 20 weeks after the last dose of study intervention).
- A WOCBP must have a negative highly sensitive pregnancy test (urine or serum as required by local regulations) on Day 1 before the first dose of study intervention.
- If a urine test cannot be confirmed as negative (eg, an ambiguous result), a serum pregnancy test is required. In such cases, the participant must be excluded from participation if the serum pregnancy result is positive.

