9.2.5 Multiplicity adjustment

Multiplicity is considered for the significance testing of multiple efficacy endpoints. The overall Type-I error rate will be controlled at the 2-sided 0.05 level.

As a nonbinding futility IA is planned for the study (see [Section 9.3](#)), an administrative penalty of $\alpha = 0.001$ will be taken from the significance level used at final analysis; that is, a 2-sided $\alpha = 0.049$ will be used for the final primary efficacy analysis. No further multiplicity adjustment will be performed for the IA.

At the final analysis, the family-wise Type I error rate for testing multiple hypotheses pertaining to the primary endpoint and secondary endpoints will be strongly controlled using a gate-keeping procedure. The procedure starts with testing the co-primary endpoints between 300 mg Q2W and placebo at the 2-sided 0.049 significance level. If both co-primary endpoints are significant, then the co-primary endpoints for 300 mg Q4W, the key secondary endpoints and a selective set of secondary endpoints including the efficacy endpoints on asthma and AERD sub-populations for both doses will be tested using a prespecified multiplicity testing procedure with the overall Type I error rate being controlled at 0.049 level among the multiple endpoints and the comparisons between each dose (300 mg Q2W or 300 mg Q4W) and placebo. The complete list of the endpoints and the multiplicity testing procedure will be specified in the SAP.

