9.4 SAMPLE SIZE DETERMINATION

Approximately 210 participants will be randomized in 1:1:1 ratio to investigational intervention groups.

The sample size calculations are based on the co-primary endpoints NPS and NCS. The planned sample size is approximately 70 participants per study intervention group. With a two-sample t-test at a two-sided significance level of $\alpha = 0.049$, this sample size will provide:

- 95% power to detect a -1.10 difference for change from baseline in NPS at Week 24 between itepekimab and placebo and a common SD of 1.79. The minimal detectable difference is around -0.60.
- 95% power to detect a -0.55 difference for change from baseline in NCS at Week 24 between itepekimab and placebo and a common SD of 0.9. The minimal detectable difference is around -0.30.

The combined power of the 2 co-primary efficacy endpoints is at least 90% assuming no negative correlation between the 2 endpoints.

Differences of -1.10 and -0.55 in NPS and NCS from placebo are considered clinically relevant (54). The common SDs were estimated from LIBERTY NP SINUS-24 and SINUS-52 trials with dupilumab (NCT02912468; NCT02898454).

For the key secondary endpoints of change from baseline in NPS and NCS at Week 52, the study will have a 95% power to detect the same treatment differences as for the co-primary endpoints with the same assumed common SDs based on a two-sided α level of 0.049.

Note that as the primary analyses will be performed based on the ITT population with the dropouts (ie, one of the intercurrent events) handled using the treatment policy strategy and missing data imputed using the MI method, the sample size calculations were performed on all randomized participants. In other words, the detectable treatment differences stated above are for ITT population including early dropouts. Very low dropout rates (<5%) were observed from LIBERTY NP SINUS-24 and SINUS-52 studies (NCT02912468; NCT02898454), therefore the impact on the treatment effects is expected to be minimal.

Calculations were made based on two-sample t-test using nQuery Advisor 9.2.1.0.

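### The negative binomial and Cox models for SCS or surgery are valid but leave unused the recorded history of prior SCS courses and sinonasal surgery; adding both is a cheap efficiency gain of unknown size

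*Protocol*

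**What the plan says.** Protocol section 9.2.3 names the terms of both event models, and the synopsis repeats them.

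- Annualized number of SCS courses or surgery for CRS: negative binomial regression "with intervention group, asthma/AERD strata and regions. Log transformed treatment duration will be the offset variable".
- Time to first SCS use or surgery for CRS: Cox regression in which "intervention group, asthma/AERD strata and region will be used as covariates".
- Versions in participants with AERD: the same models without the asthma/AERD term, which leaves treatment and region.

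The history of the same kinds of event is collected before randomisation. Schedule of Activities footnote g has the eCRF hold "SCS use (number of courses, doses, way of administration and duration) in the past 2 years before Visit 1", SCS contraindication or intolerance, and the type and dates of past sinonasal surgeries. Inclusion criterion I 03 makes "Prior sinonasal surgery for NP" one route to eligibility. The other two are SCS-treated worsening within 2 years, and worsening that would have needed SCS in someone who cannot take them. Section 6.3 stratifies only by asthma/AERD status and region, so neither history enters the models through the strata.

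**The concern.** The endpoint counts or times SCS courses and surgery for CRS. A participant's past courses and past surgery are natural candidates to predict it, and the three routes in I 03 ensure that these histories differ between participants. The continuous endpoints are adjusted for their own baseline value; the event endpoints have no comparable term.

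If the histories are prognostic, leaving them out has two different effects. In the negative binomial model, between-participant variation that could be explained stays in the dispersion, and the standard error of the log rate ratio is larger than it need be. In the Cox model, the hazard ratio is averaged over the histories and lies closer to 1 than the hazard ratio at fixed history, so the test has less power. In both, a chance imbalance in history between arms of about 70 stays in the estimate as ordinary sampling error. At stake is efficiency on secondary endpoints, not validity.

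**Working it through.** **Design figures.** Section 9.4 says "The planned sample size is approximately 70 participants per study intervention group", with two-sided alpha 0.049. The section's power statements reproduce with power = Φ(δ/σ × √(n/2) − z), where z = 1.969 and √(70/2) = 5.916:

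- NPS: 1.10/1.79 × 5.916 = 3.636; 3.636 − 1.969 = 1.667; power 95.2% (95.0% with the noncentral t).
- NCS: 0.55/0.9 × 5.916 = 3.615; 3.615 − 1.969 = 1.646; power 95.0% (94.8% with the noncentral t).

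These match the stated 95% and are untouched by this point. For the SCS or surgery endpoints the protocol states no event rate, rate ratio, hazard ratio or power, so there is no planned figure to reproduce.

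**Simulation.** From the protocol: three arms of 70, alpha 0.049, AERD share about 25%, and 5% dropout (the protocol cites under 5% in earlier trials). Assumed, with no support in the protocol:

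- placebo rate 0.3, 0.6 or 1.0 events per year; rate ratio 0.5; gamma dispersion 0.5
- prior surgery in 60%; prior courses Poisson with mean 1, capped at 4; anyone with neither history given one course, to respect I 03
- log-rate shifts of 0.2 and 0.4 for asthma only and for asthma with AERD
- event-rate multipliers per prior course / for prior surgery of 1.0/1.0, 1.3/1.3, 1.6/1.8 or 2.0/2.0

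Each setting had 500 trials. Each model was fitted with the protocol's terms and again with prior courses and prior surgery added. SE ratio is the adjusted standard error over the unadjusted one; arrows run from unadjusted to adjusted.

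| Placebo rate | Multipliers | NB SE ratio | NB power | Cox SE ratio | Cox log HR | Cox power |
|---|---|---|---|---|---|---|
| 0.3 | 1.0/1.0 | 1.002 | 0.412→0.414 | 1.005 | −0.698→−0.705 | 0.356→0.362 |
| 0.3 | 1.3/1.3 | 1.001 | 0.398→0.414 | 1.006 | −0.720→−0.727 | 0.368→0.374 |
| 0.3 | 1.6/1.8 | 0.985 | 0.354→0.372 | 1.008 | −0.704→−0.733 | 0.346→0.372 |
| 0.3 | 2.0/2.0 | 0.957 | 0.340→0.380 | 1.014 | −0.652→−0.699 | 0.288→0.330 |
| 0.6 | 1.0/1.0 | 1.001 | 0.648→0.654 | 1.005 | −0.667→−0.670 | 0.540→0.544 |
| 0.6 | 1.3/1.3 | 0.993 | 0.630→0.650 | 1.006 | −0.668→−0.681 | 0.554→0.572 |
| 0.6 | 1.6/1.8 | 0.961 | 0.604→0.648 | 1.009 | −0.624→−0.657 | 0.468→0.518 |
| 0.6 | 2.0/2.0 | 0.911 | 0.562→0.654 | 1.014 | −0.590→−0.648 | 0.418→0.476 |
| 1.0 | 1.0/1.0 | 1.000 | 0.838→0.842 | 1.005 | −0.629→−0.634 | 0.658→0.650 |
| 1.0 | 1.3/1.3 | 0.987 | 0.794→0.808 | 1.006 | −0.593→−0.610 | 0.592→0.606 |
| 1.0 | 1.6/1.8 | 0.944 | 0.752→0.812 | 1.009 | −0.584→−0.625 | 0.540→0.580 |
| 1.0 | 2.0/2.0 | 0.882 | 0.652→0.756 | 1.012 | −0.553→−0.615 | 0.504→0.554 |

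**Reading it.**

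- Negative binomial: the SE ratio runs from 1.00 to 0.88. The participant equivalent is 1/ratio² − 1; the strongest setting gives 1/0.882² − 1 = 28.5%, the setting without prognostic value about 0%. Power gains run from 0.2 to 10.4 points.
- Cox: the SE ratio is above 1 throughout (1.005 to 1.014). Power changes run from −0.8 points (no prognostic value) to +5.8 points, because the log hazard ratio moves further than its standard error grows.
- Each power figure has a Monte Carlo standard error of up to √(0.5 × 0.5/500) = 2.2 points. Adjusted and unadjusted fits share the same trials, so their differences are steadier than that, but gains of a point or so should not be read closely.
- Average events over all three arms were 41 to 137 for the count model and 32 to 87 first events for the Cox model.

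**AERD versions.** 25% of 210 is about 52 participants, or about 17 per arm. Two extra parameters are a real burden there.

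**The case against.** The best reply is that nothing here is wrong. Both models contain the randomisation factors and are valid, and which further covariates to add is a matter of judgement. That stands. The contrast with the continuous endpoints is no contradiction either, since an event count has no baseline measurement on the same scale, and asthma/AERD status already carries some severity information.

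A reader might infer that both models lose precision. The protocol and the calculation do not support this for the Cox model, whose standard error rises slightly on adjustment. Nor is its unadjusted hazard ratio biased: adjusted and unadjusted hazard ratios are different quantities, and any gain is in power.

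A reader might also infer a known, material loss. The protocol gives no event rates and no evidence of how far past SCS or surgery predicts later use; with modest multipliers the gain is almost nil.

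The covariates are also less clean than they look. Footnote g does not limit SCS use to CRS, so asthma courses may be counted. I 03 admits people who could not take SCS and may show zero courses despite qualifying worsening. Prior surgery has no look-back limit. These objections stand and shape the fix.

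Finally, these are not key secondary endpoints, they do not drive the sample size, and the SAP will add detail. That lowers the priority. But section 9.2.3 does name the model terms itself, and section 9.2.5 places AERD efficacy endpoints among those to be tested under alpha control, with the full list left to the SAP.

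**Conclusion.** The omission is certain: both models adjust only for treatment, asthma/AERD stratum and region, and leave aside history already collected. Its cost is uncertain. Under the assumed rates and prognostic strengths, the negative binomial standard error would fall by about 0 to 12% with about 0 to 10 points more power; the Cox comparison would gain about 0 to 6 points of power with a standard error 0.5 to 1.4% larger. The low end applies if the histories predict little.

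This is a cheap improvement to valid analyses and not a correction of an error. Confidence is high in the omission and low in its size.

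**What to change.** Before unblinding, add to both models, in section 9.2.3 and the synopsis:

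- the number of SCS courses in the 2 years before Visit 1, counting courses for CRS where the indication is recorded, with a stated coding for participants with SCS intolerance or contraindication;
- prior sinonasal surgery (yes/no).

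For the AERD versions, fix the fallback in advance, for example dropping both covariates. A bare condition that the model converges leaves the choice open until the data are seen. State that the Cox hazard ratio is conditional on the added covariates.

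The cost is a line or two of text, plus the coding rules; footnote g already requires the data. The downsides are the changed meaning of the hazard ratio and two more parameters fitted to modest event counts.
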